10.3 Exploratory Endpoints

To evaluate the use of NM PET/CT vs CT imaging in PTCL, the endpoint will be a review of the utilized imaging modalities during treatment as a tool of response assessment. When both imaging modalities are chosen for a patient, response assessment will be compared using Kappa statistics.

To validate a new prognostic model for newly diagnosed PTCL.[41], the endpoint will be clinical biomarkers including age, race, histology, and stage as an assessment of prognosis. These factors will be related to response and survival using logistic regression and proportional hazards regression respectively.

To investigate the tumor immunohistochemical profile to identify potential, biomarkers associated with prognosis and treatment response, immunohistochemical profiles with related to treatment outcomes on archived tissue samples using the regression methods described above.

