3.0 Patient Eligibility

The target population for this phase II study is patients with histologically confirmed (previously untreated) peripheral T-cell lymphoma (PTCL). Northwestern University will serve as the lead site and coordinating center for this study. Participating sites will include Weill Cornell Medical College, and City of Hope.

A total of 20 evaluable subjects will be needed for this trial; up to 35 may be accrued to obtain 20 who are evaluable. Approximately 3 potentially eligible patients are seen per month, and it is anticipated that at least 1 per month will be accrued (once all sites are up and running). Potential patients may be referred to the Principal Investigator (PI) at Northwestern University, , or to the local PI at each participating site.

Eligibility will be evaluated by the study team according to the following criteria. Eligibility waivers are not permitted. Subjects must meet all of the inclusion and exclusion criteria to be registered to the study. Study treatment may not begin until a subject is registered. After registration, treatment should begin with 14 days. Please refer to Section 11.4 for complete instructions regarding registration procedures.

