9.3.1 Technique

A tissue microarray (TMA) of paraffin-embedded lymphoid tissue biopsies of all patients will be created and analyzed. This TMA will quantify expression of multiple markers in order to determine how such markers correlate with clinical outcome. Proposed analysis includes immunohistochemistry for CD4, CD8, CD5, CD7, CD8, CD15, CD20, CD30, EBER, Ki-67, p53, TIA-1, granzyme B, TCR F1, TNF-α, IL-6, and nm23-H1.

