10.0 Statistical Considerations

10.1 Primary Endpoint & Sample Size Calculations

The primary objective of this phase II trial will be to evaluate the efficacy of the combination of romidepsin plus lenalidomide in patients with previously untreated PTCL. The endpoint for this objective will be objective response rate (ORR), defined per Cheson criteria. Response will be assessed by imaging after cycles 3 and 6, and then every 6 months thereafter. Single agent romidepsin or lenalidomide have response rates of approximately 25% in patients with relapsed/refractory PTCL [3, 44, 45]. However, a recently presented study (unpublished) of the combination of romidepsin and lenalidomide demonstrated an objective response rate in relapsed/refractory PTCL of 50%[46]. The front-line setting has not been tested.

Due to recruitment issues, we will limit the study to n=20 evaluable patients. This will allow us to estimate the underlying true response rate with a half width of an approximate 95% confidence interval equal to 1.96x0.5/sqrt(20) = 1.96x0.11 = 0.22.

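### Section 10.3 relates 16 tissue markers to outcome by logistic and Cox regression in at most 20 patients, with marker scoring and model form unstated, so some estimates may not exist and chance findings would be hard to judge

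*Combined protocol and SAP*

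**What the plan says.** Section 9.3.1 describes a tissue microarray built from stored biopsies. The list begins "Proposed analysis includes immunohistochemistry for CD4, CD8, CD5, CD7, CD8, CD15, CD20, CD30, EBER, Ki-67, p53, TIA-1, granzyme B, TCR F1" and continues with TNF-α, IL-6 and nm23-H1. That is 17 entries and 16 distinct markers, because CD8 appears twice. On the scale of measurement it says "This TMA will quantify expression of multiple markers", with no scoring rule or cut-point.

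Section 10.3 gives the marker analysis in one clause: profiles are related to outcomes "using the regression methods described above". The reference is to the preceding paragraph on the prognostic model: "These factors will be related to response and survival using logistic regression and proportional hazards regression respectively".

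On numbers, section 10.1 says "we will limit the study to n=20 evaluable patients", while section 3.0 says "up to 35 may be accrued to obtain 20 who are evaluable". Under section 4.6, patients who leave before two cycles for reasons other than progression or toxicity do not count for efficacy, so outcome analyses rest on 20 patients. Sections 3.1.1, 6.3.3 and 9.3.2 require stored tissue where it exists but admit patients without it, so the marker set may be smaller than 20.

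For these analyses the plan gives no significance level, no rule for the number of comparisons, no choice between single-marker and joint models, no method for sparse data, and no rule on which results are reported.

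**The concern.** Two things can go wrong when many markers are screened in about 20 patients.

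First, maximum likelihood can fail. If every marker-positive patient responds, or none does, the logistic odds ratio estimate is infinite (quasi-complete separation) and its Wald p-value is uninformative. Cox regression has the same weakness when one marker group has no events. The rarer the positive category, or the more markers in one model, the more often this happens.

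Second, with many marker-outcome pairs, some will look notable by chance. If only those are reported, a reader cannot tell how many were tried.

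Objective 2.3.3 is to identify candidate biomarkers of prognosis and response. What is at stake is whether its output can be used to choose markers for later study.

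**Working it through.** **The plan's own figure.** Section 10.1 gives a 95% half-width for the response rate: 1.96 × 0.5/√20 = 0.219, which rounds to the stated 0.22. It is the only sample-size figure; none is given for the biomarker objective.

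**Inputs from the documents.** Markers: 16 (9.3.1). Outcomes: response and survival (10.3), so 16 × 2 = 32 pairs, or 48 if PFS and OS are analysed separately. Patients: 20 (10.1). Response rate: 50%, the relapsed/refractory figure in 10.1; section 1.4 also gives 66%, in six patients.

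**Assumptions, shown as ranges.** Marker prevalence 10% to 50% if binary; correlation between tests 0 to 0.7; a 5% two-sided level per test; markers unrelated to outcome.

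**1. One binary marker, positives fixed.** With 10 responders among 20 and m positive patients, the chance that all positives fall in one outcome group is 2 × C(20−m, 10−m)/C(20, 10):

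- m = 1: 2 × 92,378/184,756 = 1
- m = 2: 2 × 43,758/184,756 = 0.474
- m = 3: 2 × 19,448/184,756 = 0.211
- m = 4: 2 × 8,008/184,756 = 0.087

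**2. Sixteen binary markers, fitted singly.** Exact enumeration of 2×2 tables at n = 20 and a 50% response rate gives the per-marker chance f that the odds ratio does not exist (zero cell or no variation). The chance of at least one failure is 1 − (1 − f)^16, with markers taken as independent.

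| Prevalence | f | At least one of 16, response 50% | Same, response 66% |
|---|---|---|---|
| 10% | 0.60 | >99.9% | >99.9% |
| 20% | 0.232 | 98.5% | 99.6% |
| 30% | 0.077 | 72% | 90% |
| 50% | 0.013 | 18.5% | 55% |

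If only 15 patients have tissue (assumed), the 50%-response figures at 20%, 30% and 50% prevalence become 99.9%, 95% and 58%.

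**3. Continuous markers, fitted singly.** Cover's counting formula for one untied covariate plus intercept gives 2 × (1 + 19)/2^20 = 0.000038 per marker. For 16 markers the chance is at most 16 × 0.000038 = 0.0006, or 0.06%.

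**4. All 16 markers in one logistic model.** The same formula gives 1 − 2 × (C(19,17) + C(19,18) + C(19,19))/2^20 = 1 − 2 × (171 + 19 + 1)/1,048,576 = 0.9996. Separation is almost certain.

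Steps 1 to 4 concern logistic regression. The documents give no event count, so the Cox equivalent is not quantified.

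**5. False leads at an assumed 5% level.** Expected number over 32 tests: 32 × 0.05 = 1.6. Chance of at least one if independent: 1 − 0.95^32 = 0.806. Simulation with equally correlated normal test statistics gives 68%, 52% and 35% at correlation 0.3, 0.5 and 0.7. For response alone (16 tests) the figure is 1 − 0.95^16 = 56% if independent, and 48%, 37% and 26% at the same correlations.

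**6. Actual test size at n = 20.** Wald tests in sparse tables rarely reject: over the 16 binary response tests the chance of at least one rejection is 1% to 43% for prevalence 10% to 50%, against 58% to 75% with likelihood-ratio tests. Simulating 16 logistic and 16 Cox fits with independent markers gives 66% to 72% (Wald) or 88% to 89% (likelihood ratio).

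**The case against.** The strongest reply has four parts.

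*The only scale mentioned is quantitative.* Section 9.3.1 speaks of quantifying expression and sets no positive/negative call. Continuous markers fitted singly almost never separate. A reader might infer from the sample size that some estimates are bound to be missing, but the documents do not support that: it needs low-prevalence binary scoring or one joint model, and the plan specifies neither. This part stands. What remains is that the plan excludes neither, and the answer runs from near 0 to near 100% across choices left open.

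*No threshold is set.* A reader might also infer that a false lead is more likely than not. That rests on a 5% rule absent from section 10.3 and on weak to moderate correlation. Response and survival come from the same patients, so independence is not a natural base case; at correlation 0.7 the figure is 35%, and for response alone with Wald tests it is below 50%. The two problems also partly offset each other, since a separated marker tested by Wald almost never looks significant. This part stands too, so the figures are conditional.

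*The plan names a model class, not a fitting method.* Penalised fitting is not ruled out. True, but maximum likelihood is the usual reading when nothing else is said.

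*The work is labelled exploratory.* Formal error control is therefore a matter of preference, and estimates with intervals are a legitimate alternative. This is accepted for multiplicity adjustment. It does not make an infinite odds ratio interpretable, nor tell a reader how many markers were examined.

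**Conclusion.** The point holds as a low-cost improvement to an exploratory analysis. Section 10.3 relates 16 markers to response and survival in at most 20 patients with methods that may or may not yield estimates, depending on marker scoring and model form. The logistic failure chance is at most 0.06% for continuous markers fitted singly, 72% to 98.5% for binary markers at 30% to 20% prevalence, and 99.96% for a joint model, all at an assumed 50% response rate. The false-lead chance over 32 pairs is about 81% if independent and 35% to 68% at correlation 0.7 to 0.3, if each pair were judged at 5%. Prevalence, correlation and the 5% level are assumptions, not figures from the plan.

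No primary or secondary conclusion depends on this analysis, so the point should not be read as casting doubt on the response-rate estimate.

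**What to change.** In section 10.3:

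- Fit one marker at a time, with Firth-penalised logistic regression for response and Firth-penalised Cox regression for survival, and profile-likelihood intervals. These give finite estimates when a cell is empty. A marker with no variation should be listed as not estimable.
- Keep quantified markers on their measured scale. Dichotomising them for Fisher or log-rank tests creates the sparse cells at issue and cannot rescue rare markers: with 10 responders in 20, Fisher's two-sided p-value cannot fall below 0.21 with 3 positives or 0.087 with 4.
- State the analysis set (efficacy-evaluable patients with adequate tissue) and the scoring of each marker.
- Report every marker tested with its interval, give the number of marker-outcome pairs examined, and describe the results as hypothesis-generating.

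Benjamini-Hochberg adjusted values may be added but are optional. Strict control would cost much at this size: for a 10 v 10 marker split and response 20% v 80%, power falls from 82% at 0.05 to 27% at the Bonferroni level 0.05/32 = 0.0016, a harsher rule than Benjamini-Hochberg and shown only for scale.

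The cost is a few sentences and standard software, with no new data, visits or patients. The downside is slightly shrunken estimates and fewer nominally notable markers.

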11.0 Study Management

11.1 Conflict of Interest

All investigators will follow the Northwestern University conflict of interest policy.

11.2 Institutional Review Board (IRB) Approval and Consent

It is expected that the IRB will have the proper representation and function in accordance with federally mandated regulations. The IRB should approve the consent form and protocol.

In obtaining and documenting informed consent, the investigator should comply with the applicable regulatory requirement(s), and should adhere to Good Clinical Practice (GCP) and to ethical principles that have their origin in the Declaration of Helsinki.

Before recruitment and enrollment onto this study, the patient will be given a full explanation of the study and will be given the opportunity to review the consent form. Each consent form must include all the relevant elements currently required by the FDA Regulations and local or state regulations. Once this essential information has been provided to the patient and the investigator is assured that the patient understands the implications of participating in the study, the patient will be asked to give consent to participate in the study by signing an IRB approved consent form.

Prior to a patient's participation in the trial, the written informed consent form should be signed and personally dated by the patient and by the person who conducted the informed consent discussion.

11.3 Required Documentation (for multi-site studies)

Before the study can be initiated at any external participating sites, the following documentation must be provided to the Clinical Trials Office (CTO) at NU.

- A copy of the official IRB approval letter for the protocol and informed consent
- CVs and medical licensure for the principal investigator and any associate investigators who will be involved in the study
- Form FDA 1572 appropriately filled out and signed with appropriate documentation
- A copy of the IRB approved consent form
- Executed clinical research contract

11.4 Registration Procedures

Patients may not begin protocol treatment prior to registration. All patient registrations will be registered centrally through the Clinical Trials Office (CTO) at Northwestern University before enrollment to study. In order for registrations to be processed efficiently, staff are asked to inform the QAM of date and time that by which the patient will need to be registered. Please contact the assigned Quality Assurance Monitor (QAM) or email the QA Department ([contact]) for questions regarding patient registration.

Prior to registration, eligibility criteria must be confirmed by the assigned QAM. The study coordinator will screen all subjects for potential registration via the web-based application NOTIS (Northwestern Oncology Trial Information System), which is available at: https://notis.nubic.northwestern.edu. Please note that a username and password is required to use this program, and will be provided during site activation prior to training on the NOTIS system.

BEFORE a patient can be treated on study, please complete and submit the following items to confirm eligibility and receive an identification number:

- Patient's signed and dated informed consent form (upload to NOTIS and keep original hard copy in a secure location/study chart)
- Eligibility checklist (signed and dated by the treating physician upload to NOTIS)
- Eligibility eCRF (complete in NOTIS)
- Copy of the pathology report (upload to NOTIS)

Training on eCRF completion will be provided at the time of site activation. Please refer to the eCRF demonstration videos on the CTO website for additional instructions on registering a patient.

The QAM will review the registration, register the patient, assign a subject identification number, and send a confirmation of registration to study personnel. Registration will then be complete and the patient may begin study treatment.

11.5 Data Management and Monitoring/Auditing

This study will be conducted in compliance with the Data Safety Monitoring Plan (DSMP) of the Robert H. Lurie Comprehensive Cancer Center of Northwestern University (please refer to the DSMP hyperlink for additional information). The level of risk attributed to this study requires High Intensity Monitoring, as outlined in the DSMP. The assigned Quality Assurance Monitor, with oversight from the Data and Safety Monitoring Committee, will monitor this study in accordance with the study phase and risk level. Please refer to NOTIS for additional data submission instructions.

11.6 Adherence to the Protocol

Except for an emergency situation in which proper care for the protection, safety, and well-being of the study patient requires alternative treatment, the study shall be conducted exactly as described in the approved protocol.

11.6.1 Emergency Modifications

Investigators may implement a deviation from, or a change of the protocol to eliminate an immediate hazard(s) to trial subjects without prior IRB approval.

For any such emergency modification implemented, an IRB modification form must be completed within five business days of making the change, and the QAM must be notified within 24 hours of such change.

11.6.2 Other Protocol Deviations

All other deviations from the protocol must be reported to the assigned QAM using the appropriate form.

A protocol deviation is any change, divergence, or departure from the study design or procedures of a research protocol that is under the investigator's control and that has not been approved by the Institutional Review Board (IRB). Protocol deviations must be reported according to the policies and procedures of the IRB of record.

An unplanned protocol variance is considered a violation and may be considered an instance of Reportable New Information (RNI) if the variance:

- Has harmed or increased the risk of harm to one or more research participants.
- Has compromised the rights and welfare of the research subject
- Has damaged the scientific integrity of the data collected for the study.
- Results from willful or knowing misconduct on the part of the investigator(s).
- Demonstrates serious or continuing noncompliance with federal regulations, State laws, or University policies.

11.7 Amendments to the Protocol

Should amendments to the protocol be required, the amendments will be initiated and maintained by the assigned Medical Writer. Requests for revisions may come from multiple sources, including but not limited to the Principal Investigator, study team, drug company, or FDA. It should also be noted that when an amendment to the protocol substantially alters the study design or the potential risk to the patient, a revised consent form might be required.

All amendments will be subject to the review and approval of the appropriate local, institutional, and governmental regulatory bodies, as well as by Celgene. Amendments will be distributed by the lead institution (Northwestern) to all affiliate sites upon approval by the Northwestern University IRB.

11.8 Record Retention

Study documentation includes all eCRFs, data correction forms or queries, source documents, Sponsor-Investigator correspondence, monitoring logs/letters, and regulatory documents (e.g., protocol and amendments, IRB correspondence and approval, signed patient consent forms).

Source documents include all recordings of observations or notations of clinical activities and all reports and records necessary for the evaluation and reconstruction of the clinical research study.

Government agency regulations and directives require that the study investigator must retain all study documentation pertaining to the conduct of a clinical trial. In the case of a study with a drug seeking regulatory approval and marketing, these documents shall be retained for at least two years after the last approval of marketing application in an

International Conference on Harmonization (ICH) region. In all other cases, study documents should be kept on file until three years after the completion and final study report of this investigational study.

11.9 Obligations of Investigators

The Principal Investigator is responsible for the conduct of the clinical trial at the site in accordance with Title 21 of the Code of Federal Regulations and/or the Declaration of Helsinki. The Principal Investigator is responsible for personally overseeing the treatment of all study patients. The Principal Investigator must assure that all study site personnel, including sub-investigators and other study staff members, adhere to the study protocol and all FDA/GCP/NCI regulations and guidelines regarding clinical trials both during and after study completion.

The Principal Investigator at each institution or site will be responsible for assuring that all the required data will be collected and entered onto the Case Report Forms. Periodically, monitoring visits will be conducted and the Principal Investigator will provide access to his/her original records to permit verification of proper entry of data. At the completion of the study, all case report forms will be reviewed by the Principal Investigator and will require his/her final signature to verify the accuracy of the data.

11.10 Publication Policy

All potential publications and/or data for potential publications (e.g. manuscripts, abstracts, posters, clinicaltrials.gov releases) must be approved in accordance with the DSMC Data Release Policies and Processes. The assigned QAM will prepare a preliminary data set for DSMC approval no later than 3 months after the study reaches its primary completion date, as defined by ClinicalTrials.gov. This is the date that the final patient was examined or received an intervention for the purposes of final collection of data for the primary outcome, whether the clinical trial concluded according to the prespecified protocol or was terminated. If the investigator would like data release to be approved by the DSMC prior to when study design specifies, and/or prior to three months after a study's primary completion date, the PI must send a written request for data approval to the QAM which includes justification. Requests must be made a minimum of six to eight weeks in advance of the expected deadline. The request will be presented to the DSMC at their next available meeting. Any DSMC decisions regarding data release will be provided to the PI. If the request is approved, the QAM will present the data set to the DSMC for approval. A final, DSMC-approved dataset, as applicable, will then be released 6-8 weeks after the request was made. The investigators are expected to use only DSMC-approved data and statistical analyses any time they are disseminating trial data. The investigators must send a copy of the draft abstract/poster/manuscript to the study's biostatistician and assigned QAM to confirm that the DSMC-approved data and statistical analyses are used appropriately. Once the biostatistician and QAM gives final approval, the publication may be submitted to external publisher.

